### Statistical Analysis

Fisher tests will be used to evaluate for differences in categorical variables and a 2-tailed t-test and Mann-Whitney-U (MWU) test will be used for assessing differences between normally distributed continuous data and non-normally distributed continuous data, respectively. The data will be analyzed using R statistical analysis software.

The change in IBS-SSS score from baseline will be computed using a generalized linear mixed effect model. We will include treatment, time, and treatment x time as covariates. Tukey's honestly significant difference will be used for multiple comparisons. Data will be analyzed based on a modified intention-to-treat approach. Specifically, patients with less than one full week of data will be excluded from the study.

For all the secondary Aims, a simple 2-sample analysis (T-, MWU or Fisher's) test for changes in outcomes will be performed.

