***Secondary Aims:***

To compare the efficacy of PENFS therapy versus sham therapy on:

1. the change in mean IBS-SSS at week 8 compared to baseline.
2. the proportion of adult patients with IBS who experience at least a 50-point reduction on the IBS-SSS after 4 weeks of treatment and at the extended follow up period at week 8. These patients are considered clinical responders.
3. the proportion of adult patients with IBS who experience an improvement of  $\geq 30\%$  from baseline in weekly average of the daily worst abdominal pain scores after 4 weeks of treatment. These participants are considered a responder.
4. the change in mean weekly average of the daily worst abdominal pain scores after 4 weeks compared to baseline in adult patients with IBS.
5. the change in average weekly abdominal pain symptoms after 4 weeks of treatment and at extended follow-up (8 weeks) compared to baseline, assessed through the PROMIS Gastrointestinal Belly Pain Scale.
6. the change in average daily stool consistency after 4 weeks of treatment compared to baseline, assessed using the Bristol Stool Form Scale (BSFS).
7. the change in average weekly bowel habits after 4 weeks of treatment and at extended follow-up (8 weeks) compared to baseline, assessed through the PROMIS Gastrointestinal Constipation Scale and Gastrointestinal Diarrhea Scale.
8. the change in average weekly bloating symptoms after 4 weeks of treatment and at extended follow-up (8 weeks) compared to baseline, assessed through the PROMIS Gastrointestinal Gas and Bloating Scale.
9. the change in IBS-QOL in adult patients with IBS after 4 weeks of treatment and at extended follow-up (8 weeks) compared to baseline.
10. the change in resting cardio-autonomic tone, i.e. HRV, over 4 weeks of treatment compared to baseline.
11. the safety and tolerability of PENFS therapy versus sham therapy in adult patients with IBS.

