### **Daily Worst Abdominal Pain**

Other secondary endpoints of this study is the change in weekly average of the daily worse abdominal pain after 4 weeks of treatment compared to baseline and the proportion of patients with a ≥30% reduction from baseline in the weekly average of the daily worst abdominal pain scores after 4 weeks of treatment. A ≥30% reduction in worst abdominal pain score is a recommended primary endpoint by the Food and Drug Administration for IBS treatment trials and has been used in multiple clinical trials. As previously mentioned, if participants elect to use the SmartWatch system, the watch will deliver one question assessing daily worst abdominal pain to each participant's watch for one week prior to device placement to obtain a baseline. This daily worst abdominal pain will be measured using an 11-point numeric rating scale. The smart watch will then deliver the same question assessing daily worst abdominal pain for the duration of the study. If the participant elects to not use the SmartWatch system, then this same question pertaining to daily worst abdominal pain will be completed via an online questionnaire, for the duration of the study.

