## 9. Statistical Considerations

### Sample Size Calculation

Power calculations determined that at least 22 patients would be needed in each arm in order to achieve 95% power to detect at least a 30% reduction in worst daily abdominal pain scores. This power calculation was based on a study by Krasaelap et al, which evaluated the efficacy of PENFS on at least a 30% reduction of worst abdominal pain severity in adolescents with IBS.

We will aim for a sample size that will surpass the number needed to achieve at least 95% power, with a goal of 35 patients in each arm. We will also aim to enroll an additional 5 patients in each arm to account for potential dropouts or losses to follow-up. We will perform an interim analysis about one year after study enrollment has started or when each group has achieved completion of 22 subjects, whichever occurs first (will compare group data but not break the code). An estimate of the study profile is presented in Figure 1.

[figure not shown]

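### Fisher's exact test for the responder endpoints is valid but conservative; Boschloo's exact test would hold the same 5% level and is never less powerful

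*Combined protocol and SAP*

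**What the plan says.** Section 9, Statistical Analysis, states that "Fisher tests will be used to evaluate for differences in categorical variables". It then adds: "For all the secondary Aims, a simple 2-sample analysis (T-, MWU or Fisher's) test for changes in outcomes will be performed". Fisher's test is the only one of the three that suits a binary outcome.

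Two secondary aims are binary:

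- Aim 2 is the proportion of patients who "experience at least a 50-point reduction on the IBS-SSS after 4 weeks of treatment and at the extended follow up period at week 8", which gives two comparisons.
- Aim 3, repeated under Daily Worst Abdominal Pain, is "the proportion of patients with a ≥30% reduction from baseline in the weekly average of the daily worst abdominal pain scores" at the end of treatment, which gives one comparison.

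The Sample Size Calculation section plans "with a goal of 35 patients in each arm" and intends to "enroll an additional 5 patients in each arm to account for potential dropouts or losses to follow-up". Allocation is 1:1. The documents state no significance level, no sham or active response rate, and no power for the responder comparisons at 35 per arm. Two-tailed testing is mentioned only for the t-test.

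**The concern.** Fisher's test conditions on the total number of responders in the two arms together. The trial design fixes only the arm sizes; the total number of responders is random. With arms this small, few p-values are possible at each total, so the attainable level usually lies well below the nominal 5%.

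Boschloo's test takes the Fisher p-value as its statistic and calibrates it over the unconditional binomial model, with the arm sizes fixed. It keeps the 5% level and its rejection region contains Fisher's, so it gives up nothing in error control. At stake is power on three secondary comparisons. One of them, the pain response of at least 30%, is described in the protocol as an endpoint that the FDA recommends as primary in IBS trials.

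**Working it through.** **Inputs from the documents.** Fisher's test (Statistical Analysis); 35 per arm as the goal and 5 more per arm for dropout, so up to 35 + 5 = 40 (Sample Size Calculation); 1:1 allocation (Randomization and Masking).

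**Assumed.** Two-sided alpha 0.05, and all response rates.

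**The plan's own power figure.** The only one is 22 per arm for 95% power. It cannot be reproduced, because no rates, SD or alpha are given. If it was a comparison of two proportions, it can be solved backwards with

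n = [1.960·√(2p̄(1−p̄)) + 1.645·√(p₁(1−p₁)+p₂(1−p₂))]² / (p₂−p₁)².

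For 20% vs 71%, p̄ = 0.455 and n = (1.380 + 0.995)² / 0.51² = 21.7, rounded up to 22. The pair 30% vs 81% also gives 22. On that reading the sizing implies a difference of about 50 percentage points.

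**Method.** With arm sizes n and m, list all (n+1)(m+1) tables; at 35/35 that is 36 × 36 = 1,296. Let F(a,b) be the two-sided Fisher p-value when a and b patients respond.

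- Fisher's test rejects if F(a,b) ≤ 0.05.
- Boschloo's test rejects if F(a,b) ≤ c, where c is the largest cut-off for which the size does not exceed 0.05.
- Size = max over a common rate π of Σ Bin(a; n, π)·Bin(b; m, π) over the rejected tables.
- Power = the same sum with different rates in the two arms.

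Because Fisher's own size is below 0.05, c is at least 0.05. Boschloo's rejection region therefore contains Fisher's, and its power cannot be lower at any rates or arm sizes.

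**Maximum true size (PENFS/sham)**

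| Arms | Fisher | Boschloo |
|---|---|---|
| 35/35 | 2.94% | 4.80% (c = 0.0784) |
| 35/34 | 3.87% | 4.88% |
| 37/38 | 3.92% | 4.73% |
| 40/40 | 3.30% | 4.77% |

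**Power at 35/35, assumed rates**

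| Sham vs PENFS | Fisher | Boschloo | Gain (points) |
|---|---|---|---|
| 30% vs 60% | 62.3% | 70.1% | 7.8 |
| 35% vs 65% | 61.1% | 69.6% | 8.5 |
| 25% vs 55% | 65.6% | 72.0% | 6.4 |
| 35% vs 60% | 44.1% | 53.1% | 8.9 |
| 25% vs 65% | 89.0% | 92.5% | 3.5 |
| 20% vs 71% | 98.9% | 99.4% | 0.5 |
| 30% vs 81% | 99.0% | 99.4% | 0.4 |

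Gains are taken before rounding. On a wider grid (sham 10% to 60%), the gain at 35/35 runs from 6.1 to 9.6 points where Fisher's power is 30% to 70%, and from 2.9 to 5.9 points where it is 80% to 90%.

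**Gain in points at other arm sizes (PENFS/sham)**

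| Sham vs PENFS | 35/34 | 37/38 | 40/40 |
|---|---|---|---|
| 30% vs 60% | 5.8 | 1.0 | 3.9 |
| 35% vs 65% | 6.4 | 0.4 | 2.6 |
| 25% vs 55% | 3.8 | 2.4 | 6.0 |
| 35% vs 60% | 7.0 | 0.6 | 3.6 |

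**One table as illustration.** With 15/35 vs 7/35 responders, Fisher's p is 0.070 and Boschloo's p is 0.042. At 35/35 only tables with a Fisher p-value above 0.05 and up to 0.078 change their result.

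**The case against.** The strongest reply is that nothing here is wrong. Fisher's test is prespecified, widely used and controls type I error, and choosing between two valid exact tests is a matter of efficiency. The endpoints are secondary, the trial calls itself a pilot, and the primary analysis (a mixed model for IBS-SSS change) is untouched. All of that stands.

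The size of the gain is also conditional. A reader might infer from the 35/35 figures that the plan simply loses about 8 points of power, or that these tests run at about half the intended error rate. The documents support neither as a general statement:

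- No response rates are given. The gain is near its largest for moderate effects and almost vanishes for the very large effect that 22 per arm at 95% power would imply.
- Arms of exactly 35 are a goal. The modified intention-to-treat rule drops only patients with less than one full week of data, so arms may be unequal and may reach 40. One patient fewer in one arm lifts Fisher's maximum size from 2.9% to 3.9%.
- A fixed exchange rate in patients, such as Fisher's test needing 39 per arm to match Boschloo's at 35, does not hold either. At 25% vs 55%, Fisher's test at 39 reaches 71.0% against Boschloo's 72.0% at 35.

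What the reply does not remove is the dominance. Whatever the rates and arm sizes, Boschloo's test holds the level and has at least the power of Fisher's. Nor can the large-effect case be relied on: the sizing rests on a study in adolescents, and the Background states that there are no PENFS studies in adults with IBS.

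**Conclusion.** The point holds as an efficiency improvement on secondary endpoints. At an assumed two-sided 5% level, Fisher's maximum true size is 2.9% at 35/35, 3.9% at 35/34 and 3.3% at 40/40. Boschloo's test uses more of the 5% without exceeding it. With assumed response rates it adds about 6 to 9 points of power at 35/35 for moderate effects, about 0.4 to 7 points for the same effects at nearby or unequal arm sizes, and under 1 point at 35/35 for very large effects such as 20% vs 71%.

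A reader might go further and conclude that the planned test is invalid or that the trial's main conclusion is at risk. Neither follows: Fisher's test errs on the safe side, and the primary endpoint is analysed by another method. Only the size of the gain depends on the assumed rates; that it is never negative does not.

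**What to change.** In Section 9, Statistical Analysis:

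1. State the significance level: two-sided alpha of 0.05.
2. For secondary aim 2 (weeks 4 and 8) and aim 3 (week 4), replace Fisher's test with Boschloo's unconditional exact test, computed at the arm sizes actually analysed. Specify the two-sided Fisher p-value as its statistic. A routine that builds its two-sided version differently need not reject in every case where Fisher's test does.
3. Report the difference in response proportions with its 95% CI for each comparison.

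Make the change before any group data are compared, which means before the interim analysis (about one year after enrolment starts, or at 22 completers per group, whichever is first). The cost is a sentence or two of text and a slightly longer computation. It needs no new data or patients and leaves error control at 5% for each test.

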#### **Secondary Endpoints:**

#### **IBS-SSS Responder Rate**

In addition, one secondary endpoint of this study will be to assess the proportion of clinical responders, using the IBS-SSS. Clinical responders at the end of 4 weeks and at extended follow-up will be defined as those that have  $\geq 50$ -point decrease on the IBS-SSS score from baseline. This is based upon a study by

Francis et al that demonstrated that a reduction in 50-points correlated with clinically meaningful improvement. Another secondary endpoint is the mean change in IBS-SSS at the end of the extended follow up period at week 8 compared to baseline.

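### Secondary aims worded as mean changes can be decided by a rank test: the plan picks t-test or Mann-Whitney from the observed distribution, states no criterion and names no effect estimate (minor).

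*Combined protocol and SAP*

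**What the plan says.** Under Statistical Analysis (section 9), the protocol names a two-tailed t-test and the Mann-Whitney test and divides the continuous data between them: each "test will be used for assessing differences between normally distributed continuous data and non-normally distributed continuous data, respectively". It then sets the scope: "For all the secondary Aims, a simple 2-sample analysis (T-, MWU or Fisher's) test for changes in outcomes will be performed". The tests are applied to changes, without adjustment for the baseline value. No normality test, threshold or timing is given. Nor does the plan say whether normality is judged on raw scores or changes, per arm or pooled. No effect measure or confidence interval is named for either test.

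Two items under Secondary Aims are worded as means. Aim 1 is "the change in mean IBS-SSS at week 8 compared to baseline" and aim 4 is "the change in mean weekly average of the daily worst abdominal pain scores after 4 weeks compared to baseline in adult patients with IBS".

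The primary endpoint, week 4 IBS-SSS, has its own mixed model with treatment, time and their interaction. The sentence on that model speaks of IBS-SSS change in general, so it could also cover week 8. The sentence on secondary aims sends the same outcome to the two-sample rule. The plan does not say which applies.

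**The concern.** A t-test asks whether mean changes differ. Mann-Whitney asks whether a patient in one arm tends to rank above a patient in the other. The two questions coincide when one arm is a shifted copy of the other, and can differ when the shapes differ. Under the rule, the question put to each continuous secondary outcome is settled only after its distribution has been seen. The same PROMIS scale could be tested one way at week 4 and another way at week 8. If an aim about a mean goes to Mann-Whitney, the reader gets a p-value with no mean difference beside it. For a pilot whose estimates may inform a later trial, that estimate is a main product.

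**Working it through.** **Inputs from the documents.** 1:1 allocation; goal of 35 per arm; 22 per arm for 95% power; baseline worst pain 4 to 8 on a 0-10 scale; two-tailed t-test. **Assumed, because the documents give none:** two-sided alpha 0.05, SDs, response fractions, effect sizes, baseline correlations, and a switch triggered by Shapiro-Wilk p<0.05 in either arm.

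**The plan's own figure.** The plan says that "at least 22 patients would be needed in each arm in order to achieve 95% power", but gives no response rates, SD or alpha, so the figure cannot be reproduced. For a comparison of means it would imply d = (1.960 + 1.645) × √(2/22) = 1.09 SD. This does not bear on the choice of test; it only sets the range of sample sizes to examine.

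**Step 1: can the two tests answer different questions?** Let every sham patient improve by 0.75, and let 30% of active patients improve by 2.5 and the rest by 0. The means are equal: 0.30 × 2.5 = 0.75. With 35 per arm and 20,000 simulated trials, the t-test rejects 5.1-5.2% of the time. Mann-Whitney rejects 6.8% (SD 1) to 31.5% (SD 0.5). A significant Mann-Whitney result therefore does not establish a mean difference.

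**Step 2: error of the rule.** With identical normal arms the switching rule rejects about 5-6% of the time, so there is no material inflation there.

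**Step 3: power of the rule, 35 per arm.**

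On an IBS-SSS-like scale, 35% of active patients improve by 220 points and the others match sham (mean change -40; SDs 60 and 70). With no sham responders, Welch t has 83%, always-Mann-Whitney 68% and the rule 75%, a loss of 83 - 75 = 8 points. Keeping the 35-point gap in response but letting sham patients respond gives:
- sham 10%: Welch 73%, Mann-Whitney 68%, rule 71%
- sham 20%: 69%, 68%, 70%
- sham 30%: 67%, 68%, 68%

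With unit-SD changes and no sham responders, Welch against the rule is 54.9% and about 54% (30% respond by 2 SD), 67.4% and about 62% (30%, 2.5 SD), 76.6% and about 66% (30%, 3 SD), and 46.4% and about 36% (20%, 3 SD). The losses run from about 1 to 11 points.

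On the 0-10 pain scale (responders fall 60%, others 5%), t-test and rule on the same 3,000 trials:

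| Responders, sham / active | Noise SD 0.6: t, rule (loss) | Noise SD 1.2: t, rule (loss) |
|---|---|---|
| 0% / 20% | 69.6%, 31.3% (38.3) | 40.7%, 33.8% (6.9) |
| 0% / 30% | 93.3%, 60.4% (32.9) | 71.7%, 63.0% (8.7) |
| 10% / 40% | 78.0%, 59.8% (18.2) | 59.5%, 56.1% (3.4) |
| 20% / 50% | 67.5%, 57.5% (10.0) | 54.5%, 54.3% (0.2) |
| 40% / 70% | 63.1%, 58.0% (5.1) | 51.1%, 51.7% (-0.6) |

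**Step 4: the opposite case.** When everyone shifts by the same amount, Mann-Whitney beats the t-test: 89% against 72% for t-distributed data with 3 df, and 96% against 80% for exponential data.

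**Step 5: what baseline adjustment buys.** With equal SDs and correlation r, the variance of a change is proportional to 2(1 - r), and that of the baseline-adjusted score to 1 - r². At r = 0.3 these are 1.40 and 0.91, a ratio of 0.65. At r = 0.7 they are 0.60 and 0.51, a ratio of 0.85. The gain in precision is larger at low correlation. In simulation at 35 per arm and r from 0.3 to 0.7, the adjusted model with robust errors kept about 5% error. It matched or beat the switching rule except under heavy tails or skew at r = 0.7, where it lost 4-5 points.

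**The case against.** The rule is conventional, it concerns only secondary outcomes of a pilot, and the statisticians do not know the device codes, which limits choosing a test to favour an arm. The hypotheses section speaks of greater reduction or improvement, which need not mean a mean. Mann-Whitney is a sound choice for some of these outcomes, such as the LF/HF ratio or the 7-point stool form scale. All of this stands, and it keeps the point minor. It does not supply the missing criterion, and it does not turn a rank test into an answer about a mean.

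Three stronger readings are tempting, and the documents do not support them.
- **The plan expects two-humped changes, so the rule defeats itself.** The plan does say that "one secondary endpoint of this study will be to assess the proportion of clinical responders, using the IBS-SSS", but that is only a cut-off on a continuous score. Any single-humped distribution has a share beyond a cut-off. The responder proportions are compared between both arms, so nothing says that sham patients will not respond.
- **The loss is that of always using Mann-Whitney.** The rule switches only part of the time, so the relevant comparison is with the rule itself, as in step 3.
- **The analyst may take the smaller p-value.** The plan assigns one test to each kind of data. Taking the smaller p (6.0% error with normal data) would breach the plan. The excess rejections in step 1 are not errors under Mann-Whitney's own null hypothesis either, because those two distributions do differ.

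**Conclusion.** The point holds as a gap in specification with minor consequences. The test for each continuous secondary outcome depends on an unstated judgement about the observed distribution. Aim 4, and aim 1 unless the mixed model covers week 8, can be decided by a test that is not about means and carries no mean estimate.

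The point does not rest on type I error, which is about 5-6% with identical normal arms. Nor does it rest on a general loss of power. The loss is about 0-11 points in most scenarios examined. It exceeds that only on the pain scale with noise SD 0.6 and at most 10% sham responders, where it runs from about 18 to 38 points. It shrinks to 5-10 points there, and to about nothing elsewhere, once 20% or more of sham patients respond. Under skew or heavy tails with a common shift, it becomes a gain. All these magnitudes rest on assumed SDs, response fractions and a Shapiro-Wilk switch. The primary endpoint is unaffected.

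**What to change.** Replace the two-sample rule for continuous secondary outcomes that have a baseline measurement, and at least for those worded as mean changes, with text to this effect:

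> Each outcome is analysed with a linear model of the follow-up score on treatment and baseline score, with robust standard errors, whatever the observed distribution. The adjusted mean difference and its 95% CI are reported. Mann-Whitney on the changes is a sensitivity analysis. For outcomes listed here as strongly skewed or ordinal, the transformation or rank test, and the effect measure reported with it, are as stated in this list.

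The LF/HF ratio and the stool form scale are candidates for that list. Also state whether week 8 IBS-SSS is analysed by the mixed model or under this rule. Settle the text before the planned interim comparison of the groups.

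The cost is one paragraph of the analysis plan and no extra patients, visits or data. The statistical cost is some power where an outcome is skewed or heavy-tailed and strongly correlated with baseline: about 4-5 points at an assumed correlation of 0.7, and possibly more with more extreme tails. Imposing an unadjusted Welch test on every outcome would be a worse trade, because it gives up the 16-17 points of step 4 without the gain from baseline adjustment.

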**2. *Mandatory inclusion criteria:***

- Adults, aged 18-60 years, who are able to provide written, informed consent
- Patients must meet Rome IV criteria for IBS, confirmed by a gastroenterologist who specializes in functional GI disorders. Any of the IBS bowel habit subtypes (diarrhea, constipation, mixed bowel habits, unclassified) will be allowed.
- Average daily worst abdominal pain score between 4 and 8 (on a 0-10-point rating scale).
- Minimum of 2 days of abdominal pain/week prior to starting trial.
- At least moderate IBS symptom severity with an IBS-SSS  $\geq 175$  (total score range 0-500).

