#### **Primary Endpoint:**

#### **IBS Severity Scoring System (IBS-SSS)**

The primary aim of this study is to compare the efficacy of PENFS versus sham therapy on the improvement of symptom severity after 4 weeks of treatment in adult patients with IBS, using the IBS-SSS. The primary endpoint is the mean change in IBS-SSS at the end of week 4 compared to baseline. This questionnaire is a validated measure of IBS symptom severity and has been shown to be responsive to treatment in different studies. It assesses severity of abdominal pain, frequency of abdominal pain, severity of abdominal distention, dissatisfaction with bowel habits, and interference of IBS with daily life over a 10-day period. Each of the five categories will receive a score from 0-100, and the total IBS-SSS is calculated by taking the sum of these categories (total score range 0-500). Patients will complete the IBS-SSS at week 1, after week 4 of treatment, and at extended follow-up (after 8 weeks). The IBS-SSS will be completed in person at visit 1 and via an online survey at the end of week 4 and during the extended follow-up period at week 8. The online survey will be emailed to the patients the day it is to be completed, and a reminder email will be sent if the survey is not submitted. Improvement in symptom severity will be assessed using a mean change in IBS-SSS score from baseline to 4 weeks after treatment and from baseline to 8 weeks after treatment.

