**Table 1: Timing of PENFS vs Sham Interventions, Questionnaires, and HRV**

	Daily	Baseline	Screening (Visit 1)	End of Week 1 (Visit 2)	End of Week 2 (Visit 3)	End of Week 3 (Visit 4)	End of Week 4	8-week follow up
Consent + Enrollment		X						
History		X						
Daily Worst Abdominal Pain (via Smart Watch)	X	X (daily for 1 week)		X (daily during week 1)	X (daily during week 2)	X (daily during week 3)	X (daily during week 4)	
Daily BSFS		X (daily for 1 week)					X (daily during week 4)	
Physical			X					
PENFS vs Sham Device Placement			X	X	X	X		
Rome IV		X						
Bowel Symptom Questionnaire (BSQ)			X					
UCLA CNSR Participant Demographics			X					
IBS-SSS		X	X	X	X	X	X	X
PROMIS Questionnaires			X	X	X	X	X	X
IBS-QOL			X				X	X
HAD			X					
VSI			X				X	
Heart Rate Variability			X	X	X	X		

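### Baseline is used only by subtraction in the primary and continuous secondary analyses, which usually costs precision; separately, stool-form change pooled over IBS subtypes has no single direction of benefit

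*Combined protocol and SAP*

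**What the plan says.** **Endpoint and models.** The Primary Endpoint section states: "The primary endpoint is the mean change in IBS-SSS at the end of week 4 compared to baseline". Under Statistical Analysis, change in IBS-SSS is modelled with a generalized linear mixed effect model, and "We will include treatment, time, and treatment x time as covariates". No baseline score is listed, and the coding of time is not given. For the rest: "For all the secondary Aims, a simple 2-sample analysis", using t, Mann-Whitney or Fisher tests of change. The continuous outcomes among these are aims 1 and 4 to 10.

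**Which baseline.** The Primary Endpoint section describes one pre-treatment IBS-SSS: "The IBS-SSS will be completed in person at visit 1 and via an online survey at the end of week 4". Table 1 ("Timing of PENFS vs Sham Interventions, Questionnaires, and HRV") marks IBS-SSS in both the Baseline column and the Screening (Visit 1) column.

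**Power.** The Sample Size Calculation claims "95% power to detect at least a 30% reduction in worst daily abdominal pain scores" with 22 per arm and sets a goal of 35 per arm. It says nothing about IBS-SSS.

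**Stool form.** Secondary aim 6 and the Daily Bowel Habits section compare change in average BSFS between arms. The inclusion criteria say: "Any of the IBS bowel habit subtypes (diarrhea, constipation, mixed bowel habits, unclassified) will be allowed". Subtype is recorded at baseline with the Rome IV questionnaire, but no direction rule or subtype split is attached to BSFS.

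**The concern.** There are two separate issues.

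1. **Precision.** In a model with only arm, time and their interaction, the week-4 interaction contrast is simply the difference in mean change when time is categorical and data are complete. Subtracting baseline fixes its coefficient at 1, whereas adjustment estimates it. Validity is not at stake, since randomisation protects both estimates. What is lost is precision in a trial of 35 per arm that has no stated power margin for its primary outcome. Two gaps in wording compound this. If time were linear, the interaction would be a slope over all visits and not the week-4 contrast. The score that serves as baseline is also not fixed.

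2. **Interpretability of aim 6.** Improvement raises BSFS in IBS-C and lowers it in IBS-D. A pooled mean change therefore cancels benefit, partly or fully, according to a recruitment mix that the plan does not fix. Neither a null result nor the sign of a non-null result can then be read as evidence about benefit.

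**Working it through.** **The plan's own figure.** The 22 per arm at 95% power can be neither reproduced nor refuted, because alpha, responder rates and SD are not given. It concerns pain, so it does not bear on IBS-SSS.

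**Change-score identity.** In complete simulated data (35 per arm, six visits), the mixed model with categorical time gave a week-4 interaction of -27.195. The difference in mean change was also -27.195. With linear time the corresponding figure was -26.63.

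**Variance formula.** Let k = baseline SD / week-4 SD and r = their correlation. The variance of the baseline-adjusted estimate relative to the change-score estimate is

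(1 - r²) / (1 + k² - 2rk), multiplied by 1 + 1/66 for estimating the slope with 70 patients.

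Example at k = 1, r = 0.5: 0.75 / 1.00 × 1.015 = 0.761, a 24% saving. Power is from the noncentral t (67 df), at the standardised effect that gives the change-score test 80% (d = 0.679). All values of k and r are assumed.

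| k | r | variance ratio | power if change score has 80% |
|---|---|---|---|
| 1.0 | 0.3 / 0.5 / 0.7 | 0.660 / 0.761 / 0.863 | 93 / 89 / 85% |
| 0.8 | 0.3 / 0.5 / 0.7 | 0.796 / 0.906 / 0.996 | 88 / 84 / 80% |
| 0.7 | 0.3 / 0.5 / 0.7 | 0.863 / 0.964 / 1.015 | 85 / 81 / 79% |

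A 40,000-run simulation agreed at the corners: ratio 0.66 and power 93.1% at k = 1, r = 0.3; ratio 1.015 and power 79.3% at k = 0.7, r = 0.7.

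**Effect of the entry floor.** Eligibility requires "At least moderate IBS symptom severity with an IBS-SSS" of at least 175. Truncating a normal baseline to 175-500 multiplies its SD by q = 0.690 (assumed mean 220, SD 90) to 0.886 (mean 300, SD 75). The floor also lowers the week-4 SD and the correlation, so q is not k. With equal unselected SDs and unselected correlation rho, week-4 variance is rho²q² + 1 - rho², with k = q/SD4 and r = rho·q/SD4.

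- q = 0.690, rho = 0.7: SD4 = 0.862, k = 0.80, r = 0.56, ratio 0.936, a 6% saving.
- q = 0.886, rho = 0.3: SD4 = 0.990, k = 0.89, r = 0.27, ratio 0.714, a 29% saving.

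Over rho 0.3 to 0.7, the saving is 6 to 29% and power 82 to 91%. If the floor acts on an earlier score that correlates 0.7 to 0.85 with the analysed baseline, the saving is 13 to 32% and power 85 to 93%.

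**Unequal unselected SDs.** If the unselected week-4 SD is 1.15 times the baseline SD, the saving is 1 to 21%. At 1.3 times it runs from a 1% loss to 15%, with power of 79.5 to 86%.

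**BSFS.** Assume a true 1-point benefit in both IBS-C (up) and IBS-D (down), no effect in the other subtypes, SD of change 1 within subtype, and 35 per arm. The expected pooled difference is the IBS-C share minus the IBS-D share; power is from a simulated t-test.

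| IBS-C / IBS-D share (%) | expected difference | power |
|---|---|---|
| 35 / 35 | 0 | 5% |
| 40 / 30 | +0.1 | 7% |
| 20 / 40 | -0.2 | 11% |
| 50 / 20 | +0.3 | 19% |
| 60 / 20 | +0.4 | about 30% |
| 20 / 60 | -0.4 | about 30% |

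Within one subtype, power and 95% CI half-width are 41% and 1.16 points at 7 per arm, 65% and 0.85 at 12, and 89% and 0.62 at 21.

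**The case against.** **Precision.** The plan declares a change endpoint and analyses change. That is consistent and unbiased, and in a pilot, adjustment can be called an optional refinement. This stands as far as validity goes. It does not remove a gain that needs no new data.

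**Size.** The k = 1 rows are the most favourable and, given the floor, the least applicable. The 6% lower end depends on equal unselected SDs. Both points are right: the gain can be close to nil or a loss of 1 to 1.5%. The gain may also be small for some secondary outcomes. Daily pain is restricted on entry to 4-8; assuming normal pain with mean 5.5 to 6 and SD 1.5 to 2, the saving is 3 to 19% at equal unselected SDs, and from a 1% loss to 9% if the week-4 SD is 1.3 times larger.

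**Wording gaps.** Naming Tukey's procedure suggests that time is a factor, and the PROMIS, IBS-QOL, HADS/VSI and HRV sections equate baseline with visit 1. The intended reading is therefore probably recoverable. These are clarifications, and the main point does not rest on them.

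**BSFS.** Stool form appears in none of the six hypotheses, and aim 7 measures constipation and diarrhea on separate scales, each with a clear direction. This limits the consequence but does not make aim 6 interpretable. Subtype estimates will be imprecise, which is why intervals are proposed and not subgroup tests.

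**Conclusion.** Both parts hold.

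1. The primary and continuous secondary analyses use baseline only by subtraction (for the primary model, given categorical time and complete data). The cost is precision, not bias. A plausible variance saving from adjustment is 6 to 29%, under an assumed normal baseline cut at 175, equal unselected SDs and correlation 0.3 to 0.7. Other SD ratios lower this to about nothing or a trivial loss. Since the possible gain is material and the possible loss negligible, the change should be made.

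2. Pooled BSFS change cannot be interpreted as benefit or its absence. The 1-point shift and SD of 1 are illustrative, but the dependence of sign and size on subtype mix follows from the scale itself. Confidence in the numerical sizes is moderate, because no IBS-SSS or BSFS variance is documented.

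**What to change.** **Primary model.** Model post-baseline IBS-SSS with time as a categorical factor, adding baseline IBS-SSS and its interaction with time (or constrain the arms to a common baseline mean), and report the week-4 contrast as primary. State which pre-treatment IBS-SSS is the baseline and reconcile Table 1 with the Primary Endpoint section.

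**Continuous secondary outcomes.** Use ANCOVA with each outcome's own baseline, rank-based or transformed where non-normal. HRV has three post-baseline visits (ends of weeks 1 to 3), so keep all of them in a baseline-adjusted repeated-measures model.

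**BSFS.** Do not interpret a single pooled change. Report the treatment difference with its confidence interval separately for IBS-C and IBS-D, and describe IBS-M and IBS-U. A pre-specified direction-aligned measure combining IBS-C and IBS-D is optional.

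**Cost.** SAP wording and slightly more code. The baselines and Rome IV subtype are already collected. Adjustment uses one or two degrees of freedom and could gain almost nothing, or lose about 1.5% in variance, if k is low and r high. The subtype BSFS estimates will have wide intervals.
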